4.2.2. Treatment Period

- The Treatment Period will begin with the Baseline visit on Day 1. Study visits will also occur at Week 4, Week 8, Week 12, and Week 16.

- At the Baseline visit, eligible subjects will be randomized in a 1:1 ratio to receive either mepolizumab 100 mg SC or placebo SC.
- Study treatment will be prepared by a designated, qualified, unblinded member of the site staff who is independent of the protocol-defined study assessments (See Section 6.1).
- Study treatment will be administered by SC injection at the Baseline visit, Week 4, Week 8, and Week 12 (last dose). Each SC injection will be administered by a trained member of the site staff who is blinded to study treatment. See Section 6.1.1 for injection site instructions and study treatment administration details.
- Subjects will remain in the clinic for safety monitoring one hour after each administration of study treatment. Subjects will be observed for adverse events (AEs) including systemic reactions (i.e., allergic (type I hypersensitivity) reaction and other systemic reaction) and local injection site reactions (See Section 6.1.2).
- There are no planned dose adjustments during the study.
- The last dose of study treatment will be administered at Week 12. Study treatment will **not** be administered at Week 16. For those subjects randomized to mepolizumab, four doses will provide therapeutic coverage to Week 16 when efficacy assessments for the primary endpoint will occur. For this reason, the Week 16 visit is considered to be part of the Treatment Period while also serving as the first follow-up visit (Post-Treatment Visit 1).
- Subjects will continue to apply the same non-prescription, non-medicated (without an active ingredient) emollient twice daily. On study visit days, the subject must not apply the emollient within the 2-hour period preceding the study visit. See Section 6.10.1 for further details regarding emollient use.
- Subjects who prematurely discontinue study treatment will be followed for 8 weeks after the last dose and will be scheduled for the following visits (Section 5.4 and Table 3):
 - Early Withdrawal Visit (if the decision is made to prematurely discontinue study treatment <4 weeks after last dose of study treatment),
 - Post-Treatment Visit 1 (4 weeks after last dose of study treatment), and
 - Post-Treatment Visit 2 (8 weeks after last dose of study treatment).

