7.4.1.1. Time period and Frequency for collecting AE and SAE information

- Any SAEs assessed as related to study participation (e.g., protocol-mandated procedures, invasive tests, or change in existing therapy) or related to a GSK product will be recorded from the time a subject consents to participate in the study up to and including any follow-up contact.
- AEs will be collected from the start of Study Treatment until the follow-up contact (i.e., the Week 20 visit) (See Section [7.4.1.3](#)), at the timepoints specified in the Time and Events Table (Section [7.1](#)).
- Medical occurrences that begin prior to the start of study treatment but after obtaining informed consent may be recorded on the Medical History/Current Medical Conditions section of the CRF.
- All SAEs will be recorded and reported to GSK within 24 hours, as indicated in [Appendix 11](#).

- Investigators are not obligated to actively seek AEs or SAEs in former study subjects. However, if the investigator learns of any SAE, including a death, at any time after a subject has been discharged from the study, and he/she considers the event reasonably related to the study treatment or study participation, the investigator must promptly notify GSK.

NOTE: The method of recording, evaluating and assessing causality of AEs and SAEs plus procedures for completing and transmitting SAE reports to GSK are provided in [Appendix 11](#).

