12.3. Appendix 3: Study Phases and Treatment Emergent Adverse Events

12.3.1. Study Phases

Safety assessments and events will be classified according to the time of occurrence relative to the first dose of investigational product.

The on-treatment phase for the presentation of exposure, adverse event and concomitant medications is defined as being from the day of the first administration to the day of the last administration of study treatment + another 28 days inclusive.

Treatment Phase	Definition
Pre-Treatment	Date < IP start date
On-Treatment	Event onset date is on/after IP start date & on/before IP stop date + 28 days (IP Start Date ≤ Date ≤ IP Stop Date + 28 days)
Post-Treatment	Event onset date is after the IP stop date + 28 (Date > IP stop date + 28)
IP = Investigational Product = Study Treatment	

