12.5.2. Study Population

Extent of Exposure

 Number of days of exposure to study drug will be calculated based on the formula: Duration of Exposure in Days = (Treatment Stop Date – Treatment Start Date) + 29 Participants who were randomized but did not report a treatment start date will be categorised as having zero days of exposure. On-treatment phase will be calculated based on the formula: On-Treatment Phase = (Treatment Stop Date – Treatment Start Date) + 29

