12.6.2.1. Handling of Missing and Partial Dates

Element	Reporting Detail
General	
 • Partial dates will be displayed as captured in subject listing displays.
Adverse Events	
 • The eCRF allows for the possibility of partial dates (i.e., only month and year) to be recorded for AE start and end dates; that is, the day of the month may be missing. In such a case, the following conventions will be applied for calculating the time to onset and the duration of the event: 
 ○ Missing Start Day: First of the month will be used unless this is before the start date of study treatment; in this case the study treatment start date will be used and hence the event is considered On-treatment as per Appendix 3: Study Phases and Treatment Emergent Adverse Events. ○ Missing Stop Day: Last day of the month will be used, unless this is after the stop date of study treatment; in this case the study treatment stop date will be used. • Completely missing start or end dates will remain missing, with no imputation applied. Consequently, time to onset and duration of such events will be missing.

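### The SAP caps a partial AE stop date at the last dose, which gives impossible or shortened durations for some partial-date records (minor)

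*SAP*

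**What the plan says.** SAP 12.6.2.1 starts from the form design: "The eCRF allows for the possibility of partial dates (i.e., only month and year) to be recorded for AE start and end dates". When the day is missing, its "conventions will be applied for calculating the time to onset and the duration of the event". For a missing stop day the rule is "Last day of the month will be used, unless this is after the stop date of study treatment"; when month-end is later than that, the treatment stop date replaces it. A completely missing date is not imputed. The section does not require the imputed stop to be on or after onset, or to lie in the recorded month.

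Two other places show what the treatment stop date means. SAP 12.3.1 runs the on-treatment phase "to the day of the last administration of study treatment + another 28 days inclusive", and SAP 12.5.2 has "Duration of Exposure in Days = (Treatment Stop Date – Treatment Start Date) + 29". Both add the 28-day tail separately, so the stop date itself is the day of the last injection.

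Protocol 4.2.2 states: "The last dose of study treatment will be administered at Week 12". AE collection continues well beyond that point. Protocol 7.4.1.1 runs it to the Week 20 visit, and Protocol 5.4.1 follows subjects who stop treatment early for 8 weeks after their last dose.

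**The concern.** The cap falls at a date after which the study still collects AEs by design. Protocol 7.4.1.3 also has SAEs, AEs of special interest and AEs leading to withdrawal from treatment followed until they resolve or stabilise, so stop dates later than the last dose are expected. For those events the rule can override the month that the site did record and put the end of the event in an earlier month, possibly before its onset.

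What is at stake is derived AE duration, which the section names as one purpose of the convention. A programmer who follows the text must either produce negative durations or depart from the SAP without documentation.

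**Working it through.** **Inputs**
- Last planned dose: Week 12 (Protocol 4.2.2).
- End of AE collection: Week 20 (Protocol 7.4.1.1).
- Treatment stop date = last dose, L (SAP 12.3.1 and 12.5.2).
- Imputation rule (SAP 12.6.2.1).
- Calendar dates below are assumed for illustration. The documents give no subject-level dates.

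**The plan's own figure.** 20 − 12 = 8 weeks, or 56 days, of AE collection after the last dose. This agrees with the 8-week post-treatment visit in Protocol 4.2.3.

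**The rule as a formula.** Let O be onset, T the true stop, M the last day of the recorded stop month and S the imputed stop. Then S = M if M ≤ L, and S = L if M > L.

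- *Onset after the last dose (O > L).* T ≥ O > L and M ≥ T, so M > L and S = L < O. The stop precedes onset every time.
- *Onset by the last dose, true stop after it (O ≤ L < T).* M ≥ T > L, so S = L < T. The event is shortened.
- *True stop by the last dose (T ≤ L).* Either M ≤ L and month-end is used, or L lies in the recorded month and S = L ≥ T. No harm is done.

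**Examples**

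| Last dose | Onset | Recorded stop | Imputed stop | Stop − onset |
|---|---|---|---|---|
| 15 Jul | 10 Aug | Aug | 15 Jul | −(16 + 10) = −26 days |
| 24 Aug | 3 Sep | Sep | 24 Aug | −10 days |
| 24 Aug | 3 Oct | Oct | 24 Aug | −40 days |
| 24 Aug | 19 Aug | Sep (true 13 Sep) | 24 Aug | +5 days |
| 1 Jun (one dose only) | 8 Jun | Jun | 1 Jun | −7 days |

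The 24 August rows assume a first dose on 1 June 2017, so the last dose is 84 days later and Week 20 falls on 19 October. In the fourth row, counting both end days, the imputed duration is 6 days against a true 26.

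**Both days missing.** With a last dose on 15 July and both start and stop recorded only as August, the same section imputes a start of 1 August and a stop of 15 July, 16 + 1 = 17 days earlier. Its two rules then contradict each other.

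**Enumeration.** The rule was run over 365 first-dose dates, onset days 0 to 140, and assumed true durations of 1, 7, 14 and 28 days ending by Week 20. Every AE with onset after the last dose got a stop before onset: 20440/20440, 18250/18250, 15695/15695 and 10585/10585. That includes all 10220/10220 with onset in the 28-day on-treatment tail, at each duration. This confirms the algebra. It does not estimate how often the fault would occur in the trial.

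**Alternative reading.** If the treatment stop date meant last dose plus 28 days (Week 16 for a completer), onsets between Weeks 16 and 20 would still fail. SAP 12.3.1 and 12.5.2 do not support that reading.

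**The case against.** The strongest reply is that nothing reported is shown to depend on the affected quantity, and most of that reply stands.

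- The cap alters the stop date only. Time to onset uses the start date. On-treatment, post-treatment and treatment-emergent status (SAP 12.3.1 and 12.3.2) depend on onset, so no AE moves between tables and no count changes.
- SAP 12.6.2.1 keeps partial dates as recorded in listings, so the collected information stays visible.
- No title among Tables 3.1 to 3.26 mentions duration, and the mock profile for AEs of special interest has no duration row. This is not complete reassurance: SAP 8.2 leaves the profile's contents open-ended, and the standard shell for the AE listings is not shown. A derived duration could appear in either place, but the documents do not show that it does.

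A reader might infer more than the documents support in two ways. One is that all AEs late in treatment or in follow-up get wrong durations. Only records with the day missing, month and year present, and a month-end after the last dose come under the cap, and even then an event that ended by the last dose is not harmed. The other is to take the post-dose share of planned collection, 8/20 weeks = 40% for a completer, as an error rate. It is calendar time and says nothing about how many AEs carry a partial stop date. The study was also stopped for futility (SAP 1), and the dosing and follow-up that subjects actually had are not given.

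The reply does not remove the defect. The SAP says that it derives duration by this convention, and no other text corrects the result.

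**Conclusion.** The rule is wrong as written, and the consequence is minor. For a partial stop date, an AE that began after the last dose always receives a stop before onset, and an AE that spans the last dose is always shortened. The error in a single record can be weeks (26 days in the July–August example). The number of such records is unknown and could be zero.

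A reader might go on to infer that the safety tables or the AE classification are unreliable. The documents do not support that, because those outputs use onset dates and counts. The conclusion rests on reading the treatment stop date as the last dose, which the phase definition and the exposure formula both support.

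**What to change.** Replace the treatment-stop cap in SAP 12.6.2.1 with:

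*Missing stop day: use the last day of the recorded month or the date of the subject's last study contact (last visit or later AE follow-up contact), whichever is earlier; the imputed date must fall in the recorded stop month and not be earlier than the AE start date.*

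Last contact needs the definition in brackets because some events are followed past Week 20; a cap at the last visit could again override the recorded month.

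For a completer with a last dose on 15 July, Week 20 is 56 days later, on 9 September. An AE with onset on 10 August and stop recorded as August would then end on 31 August, 21 days after onset. In the enumeration, a simpler cap at Week 20 gave no stop before onset and no shortened duration. Durations can still be too long, because month-end is a late guess (43 days against a true 26 for the 19 August example), but the month-end convention is the SAP's own choice.

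The cost is one sentence and about one line of code. No data collection or other analysis changes.

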12.7. Appendix 7: Values of Potential Clinical Importance

12.7.1. Laboratory Values

Haematology				
Laboratory Parameter	Units	Age Category	Clinical Concern Range	
			Low Flag (< x)	High Flag (>x)
Hematocrit	Ratio of 1	12+	0.201	0.599
Hemoglobin	G/L	12+	71	199
Platelet Count	GI/L	1+	31	1499
While Blood Cell Count (WBC)	GI/L	12+	1.1	

Clinical Chemistry				
Laboratory Parameter	Units	Age Category	Clinical Concern Range	
			Low Flag (< x)	High Flag (>x)
ALT	U/L	3-12		>143 (and Total Bilirubin >43)
	U/L	13+		>239 (and Total Bilirubin >43)
Calcium	mmol/L	3+	1.50	3.24
Glucose	mmol/L	1+	2.2	27.8
Potassium	mmol/L	3+	2.8	6.5
Sodium	mmol/L	0+	120	160

Possible Hy's Law Cases				
Laboratory Parameter	Units	Category	Clinical Concern Range	
ALT, Bilirubin			ALT \geq 3xULN and Bilirubin \geq 2xULN (>35% direct)	
ALT, INR			ALT \geq 3xULN and INR > 1.5	

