3. OBJECTIVE(S) AND ENDPOINT(S)

Objectives	Endpoints
Primary	Primary

 To determine the efficacy of mepolizumab SC in subjects with moderate to severe AD 	
 Proportion of subjects who achieve treatment success defined as an Investigator's Global Assessment (IGA) score of 0 or 1 and at least a 2-grade improvement at Week 16.
Secondary	

 To estimate the efficacy of mepolizumab SC 	
 Mean percentage change in Eczema Area and Severity Index (EASI) score from baseline to each study visit. Proportion of subjects with an IGA score of 0 or 1 and at least a 2-grade improvement at each study visit.

 To describe the safety and tolerability of mepolizumab SC 	
 Incidence, frequency, and nature of adverse events (AEs) including local injection site reactions and systemic reactions. Change from baseline in laboratory parameters (hematology and chemistry) and frequency of clinically significant abnormal test results. Change from baseline in vital signs and frequency of clinically significant abnormal results. Immunogenicity as measured by anti-mepolizumab antibodies.
Exploratory	

 To further estimate the efficacy of mepolizumab SC 	
 Proportion of subjects with $\geq 50\%$ improvement in EASI from baseline to each study visit. Proportion of subjects with $\geq 75\%$ improvement in EASI from baseline to each study visit. Mean change in percent of total body surface area (% BSA) affected from baseline to each study visit. Mean change in weekly average of daily itch/pruritus numeric rating scale [NRS] score (based on Item #1 of Daily Sign and Symptom Severity Diary) from baseline to Week 16. Mean change in weekly average of daily itch/pruritus NRS score (based on Item #1 of Daily Sign and Symptom Severity Diary) from baseline to each study visit.

 To evaluate disease flare/relapse during and after treatment with mepolizumab SC 	
 Proportion of subjects who have an IGA score of 3 or 4 after achieving an IGA score of 0 or 1 and at least a 2-grade improvement during the Treatment and Follow-up Periods. Proportion of subjects who have an increase in EASI score of $\geq 25\%$ from baseline during the Treatment and Follow-up Periods.

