12.8. Appendix 8 – Liver Safety Required Actions and Follow up Assessments

Liver chemistry stopping criteria and required follow up assessments

Liver Chemistry Stopping Criteria - Liver Stopping Event	
ALT-absolute	ALT \geq 8xULN
ALT Increase	ALT \geq 5xULN but <8xULN persists for \geq 2 weeks ALT \geq 3xULN but <5xULN persists for \geq 4 weeks
Bilirubin^{1, 2}	ALT \geq 3xULN and bilirubin \geq 2xULN (>35% direct bilirubin)
INR²	ALT \geq 3xULN and INR>1.5, if INR measured
Cannot Monitor	ALT \geq 5xULN but <8xULN and cannot be monitored weekly for \geq 2 weeks ALT \geq 3xULN but <5xULN and cannot be monitored weekly for \geq 4 weeks
Symptomatic³	ALT \geq 3xULN associated with symptoms (new or worsening) believed to be related to liver injury or hypersensitivity
Required Actions and Follow up Assessments following ANY Liver Stopping Event	
Actions	Follow Up Assessments

 Immediately discontinue study treatment Report the event to GSK within 24 hours Complete the liver event CRF and complete an SAE data collection tool if the event also meets the criteria for an SAE² Perform liver event follow up assessments Monitor the subject until liver chemistries resolve, stabilize, or return to within baseline (See MONITORING below) Do not restart/rechallenge. Permanently discontinue study treatment and may continue subject in the study for any protocol specified follow up assessments (refer to Section 5.4). 	
 Viral hepatitis serology⁴ Blood sample for pharmacokinetic (PK) analysis, obtained within 4 weeks after last dose⁵ Serum creatine phosphokinase (CPK) and lactate dehydrogenase (LDH). Fractionate bilirubin, if total bilirubin \geq 2xULN Obtain complete blood count with differential to assess eosinophilia. Note: This blood sample will be sent to the central laboratory to maintain the blind while study is ongoing. Results will be provided only if unblinding of a subject's treatment assignment is required. Also note that the mechanism of action of mepolizumab leads to lowering of eosinophils.

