8.3. Clinical Laboratory Analyses

Laboratory evaluations including the analyses of Chemistry laboratory tests, Haematology laboratory tests and liver function tests will be based on GSK Core Data Standards. A scatter plot of maximum ALT vs baseline ALT, and maximum ALT vs total bilirubin will be produced. In addition, if any liver stopping or liver monitoring events occur during the study, then only listing of liver monitoring/stopping event reporting and hepatobiliary laboratory abnormalities will be produced. The details of the planned displays are in [Appendix 9](#): List of Data Displays.

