3.28.	Safety	LB3	Summary of Chemistry Shifts from Baseline Relative to Normal Range		SAC
3.29.	Safety	LB3	Summary of Emergent Chemistry Results (Relative to the Potential Clinical Concern Range)	ICH E3	SAC

Safety: Tables					
No.	Population	IDSL / Example Shell	Title	Programming Notes	Deliverable
Laboratory: Haematology					
3.30.	Safety	LB1	Summary of Haematology Changes from Baseline	ICH E3 Includes Baseline values.	SAC
3.31.	Safety	LB3	Summary of Haematology Shifts from Baseline Relative to Normal Range		SAC
3.32.	Safety	LB17	Summary of Emergent Haematology Results (Relative to the Potential Clinical Concern Range)	ICH E3	SAC
ECG					
3.33.	Safety	EG1	Summary of ECG Findings	The ECG findings to be summarized are the ECG interpretation, clinical significance of abnormal ECGs	SAC
3.34.	Safety	EG2	Summary of Change from Baseline in ECG Values by Visit	Includes Baseline values.	SAC
3.35.	Safety	EG10	Summary of Actual and Change from Baseline QTc(F) Values by Category	Category column will be replaced and created based on the information provided in the Section 8.4.1. For Anytime Post-Baseline, the highest post-baseline QTcF value and the change from baseline for this highest post-baseline QTc value is categorised	SAC
Vital Signs					
3.36.	Safety	VS1	Summary of Change from Baseline in Vital Signs	Includes Baseline values.	SAC
3.37.	Safety	VS3	Summary of Worst Case Vital Signs Results by PCI Criteria Post-Baseline Relative to Baseline		SAC

Safety: Tables					
No.	Population	IDSL / Example Shell	Title	Programming Notes	Deliverable
Immunogenicity					
3.38.	Safety	SAF_T3	Summary of Binding Antibody by Visit		SAC
3.39.	Safety	SAF_T4	Summary of Neutralising Antibody by Visit		SAC
3.40.	Safety	SAF_T5	Summary of Binding Antibody Assay Results: Highest Treatment Emergent Confirmatory Result Any Time Post Baseline		SAC

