12.9.12. ICH Listings

ICH: Listings					
No.	Population	IDSL / Example Shell	Title	Programming Notes	Deliverable
Subject Disposition					
1.	Screened	ES7	Listing of Reasons for Screen Failure	Journal Guidelines	SAC
2.	ITT	ES2	Listing of Reasons for Study Withdrawal	ICH E3	SAC
3.	ITT	SD2	Listing of Reasons for Study Treatment Discontinuation	ICH E3	SAC
4.	ITT	BL1	Listing of Participants for Whom the Treatment Blind was Broken	ICH E3	SAC
5.	ITT	TA1	Listing of Planned and Actual Treatments	IDSL	SAC
Protocol Deviations					
6.	ITT	DV2	Listing of Important Protocol Deviations	ICH E3	SAC
7.	ITT	IE3	Listing of Participants with Inclusion/Exclusion Criteria Deviations	ICH E3	SAC
Demographic and Baseline Characteristics					
8.	ITT	DM2	Listing of Demographic and Baseline Characteristics	ICH E3 Include Baseline Eosinophil Count and Fitzpatrick skin type	SAC
9.	ITT	DM9	Listing of Race	ICH E3	SAC
Prior and Concomitant Medications					
10.	ITT	CM3	Listing of Concomitant Medications	ICH E3	SAC
Exposure					
11.	Safety	EX3	Listing of Exposure Data	ICH E3	SAC

CONFIDENTIAL

205050

ICH: Listings					
No.	Population	IDSL / Example Shell	Title	Programming Notes	Deliverable
Adverse Events					
12.	Safety	AE8	Listing of All Adverse Events	ICH E3	SAC
13.	Safety	AE7	Listing of Participant Numbers for Individual Adverse Events	ICH E3	SAC
14.	Safety	AE2	Listing of Relationship Between Adverse Event System Organ Classes, Preferred Terms, and Verbatim Text	IDSL	SAC
15.	Safety	AE8	Listing of Adverse Events Leading to Withdrawal from Study / Permanent Discontinuation of Study Treatment		SAC
16.	Safety	AE8	Listing of Adverse Events Reported on the Day of Dosing		SAC
17.	Safety	AE8	Listing of All Adverse Events of Special Interest	Produced only if more than one AESI reported.	
All Laboratory					
18.	Safety	LB5	Listing of All Chemistry Laboratory Data for Participants with Any Value of Potential Clinical Importance	ICH E3	SAC
19.	Safety	LB5	Listing of All Haematology Laboratory Data for Participants with Any Value of Potential Clinical Importance	ICH E3	SAC
20.	Safety	LB14	Listing of Laboratory Data with Character Results		SAC
21.	Safety	LIVER5	Listing of Liver Monitoring/Stopping Event Reporting		
22.	Safety	LIVER13	Listing of Subjects Meeting Hepatobiliary Laboratory Criteria Post-Baseline		
ECG					
23.	Safety	EG3	Listing of ECG Values (Participants with QTcF >500 msec or Increase > 60 msec from Baseline)		SAC
24.	Safety	EG5	Listing of Abnormal ECG Findings	IDSL	SAC

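### SAP 12.7.1 flags ALT only in combination with raised bilirubin or INR, so no display is specified to count isolated ALT elevations by arm at multiples of ULN

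*SAP*

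**What the plan says.** Protocol Section 3 makes change in laboratory parameters and the "frequency of clinically significant abnormal test results" a secondary safety endpoint. SAP 2.2.2 keeps it for final reporting after termination.

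The SAP's fixed limits are in Section 12.7.1. Calcium, glucose, potassium and sodium each have limits of their own. ALT does not: its row for age 13 and over reads ">239 (and Total Bilirubin >43" (ALT in U/L; no unit is given for bilirubin). A separate block, "Possible Hy's Law Cases", adds two rows, and both also need a second abnormality.

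Two displays refer to these limits:

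- Table 3.29, "Summary of Emergent Chemistry Results (Relative to the Potential Clinical Concern Range", by arm.
- Listing 18, "Listing of All Chemistry Laboratory Data for Participants with Any Value of Potential Clinical Importance".

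Protocol Appendix 8 also uses ALT on its own. Treatment stops at 8xULN or more. It also stops on persistence at lower levels: "ALT \geq 5xULN but <8xULN persists for \geq 2 weeks", or 3x to below 5xULN for at least 4 weeks. The same appendix defines a monitoring event as ALT from 3x to below 8xULN with bilirubin below 2xULN, no attributable symptoms, and weekly monitoring feasible.

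For liver events that occur, SAP 8.3 says "then only listing of liver monitoring/stopping event reporting and hepatobiliary laboratory abnormalities will be produced".

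**The concern.** A by-arm table of chemistry results of clinical concern is where a reader would look first for a liver signal. As specified, it can show zero for ALT while a subject has been stopped, or put on weekly monitoring, because of ALT alone. The monitoring group is affected by construction, since the protocol defines it by bilirubin below 2xULN and the SAP's bilirubin-based flags need raised bilirubin. At stake is how easily the report shows an imbalance between arms in isolated ALT rises. Detection and management of the individual subject are not affected.

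**Working it through.** There is no sample-size or error-rate figure to reproduce, so the check compares rules.

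**Inputs**

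- Rule A (SAP 12.7.1, adult row): ALT >239 U/L and total bilirubin >43.
- Rule B (SAP 12.7.1, Hy's Law): ALT ≥3xULN and bilirubin ≥2xULN, with more than 35% direct.
- Rule C (SAP 12.7.1, Hy's Law): ALT ≥3xULN and INR >1.5.
- Stopping on ALT alone (Protocol Appendix 8): ≥8xULN; 5x to <8xULN for ≥2 weeks; 3x to <5xULN for ≥4 weeks.
- ULNs are not in the documents. Assumed: ALT 30, 35, 40, 45, 48, 50, 55 or 60 U/L; bilirubin 17, 20.5, 21 or 22, in the unit of the SAP's 43.

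**Step 1: logic.** A flag needs A, B or C. Each contains a condition that does not involve ALT: bilirubin >43, bilirubin ≥2xULN, or INR >1.5. If none of the three is met, no ALT value is flagged, whatever the ALT or its ULN.

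**Step 2: grid.** ALT at 3, 5, 8, 10 and 20xULN, bilirubin at 0.5, 1.0 and 1.5xULN, INR not measured:

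- Scenarios: 8 ALT ULNs × 4 bilirubin ULNs × 5 ALT multiples × 3 bilirubin levels = 480.
- Highest bilirubin in the grid: 1.5 × 22 = 33, below 43 and below 2xULN.
- Flagged: 0 of 480.

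At 8xULN the ALT half of rule A is always met in this range (8 × 30 = 240 to 8 × 60 = 480, all above 239). The bilirubin half is what removes the case.

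**Step 3: worked cases** (assumed ALT ULN 48, bilirubin ULN 21, so 3xULN ALT = 144 and 2xULN bilirubin = 42)

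| ALT | Bilirubin | INR | Rule A | Rule B or C |
|---|---|---|---|---|
| 384 (8xULN) | 10 | not measured | no (10 is not >43) | no (10 <42) |
| 192 (4xULN) | 50 | not measured | no (192 is not >239) | B met, if >35% direct |
| 192 (4xULN) | 10 | 1.6 | no | C met |

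The first case is a protocol stopping event and is not flagged. The other two show that rule A is not the only route to a flag, but every route is a combined one.

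**Step 4: where an isolated case would appear**

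| Display | What it gives | By-arm count at xULN multiples? |
|---|---|---|
| Table 3.28, "Summary of Chemistry Shifts from Baseline Relative to Normal Range" | Shift above normal | No, cut at the normal range |
| Figures 3.1 and 3.2 | Maximum ALT against baseline ALT and against maximum bilirubin | No, individual points |
| Listings 21 and 22 | Liver monitoring and stopping events; subjects meeting hepatobiliary criteria | No, listings |
| Table 3.1 | Adverse events by preferred term, if the investigator judged the result clinically significant | No, not threshold-based |
| Table 1.2 | Reasons for stopping treatment (categories not shown) | No; monitored subjects who continue treatment would not enter it |

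**The case against.** The strongest case on the other side has four parts.

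1. **Concern ranges are not stopping criteria.** No text says that they must agree. The limits in 12.7.1 are extreme throughout (haemoglobin below 71, platelets below 31, glucose above 27.8), so a gap from the protocol's action levels is a feature of the whole appendix. This stands. A reader might infer that the SAP contradicts the protocol; the documents do not support that.

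2. **The link to the endpoint is inferred.** The SAP does not say that Table 3.29 alone delivers the frequency of clinically significant results. Protocol Appendix 11 treats clinical significance of a laboratory result as the investigator's judgement, and results so judged become adverse events counted by arm. This also stands. A reader might infer that the secondary endpoint is misreported; that goes further than the text allows.

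3. **The cases are reported elsewhere.** Listing 21 covers stopping and monitoring events, which the protocol defines to include isolated ALT. The Figure 3.1 note presents that plot as a way to catch subjects who were not reported. So the tempting reading that such subjects disappear from the report is wrong. It remains true that none of these displays is specified to count by arm at xULN levels. The criteria behind Listing 22 sit in a sponsor standard that is not shown, but it is still a listing.

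4. **The effect is small.** The Figure 3.1 note implies that no liver event had been reported. About 56 subjects were planned, and the trial was stopped after an interim at about half, so a listing can be counted by hand. This limits the importance of the point but does not supply the missing count.

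**Conclusion.** The point holds as a minor reporting gap. No isolated ALT elevation, at any multiple of ULN, can be counted in Table 3.29 or trigger Listing 18. This follows from the structure of the criteria and does not depend on the ALT ULN. It assumes only that both displays use the 12.7.1 limits, which are the only such limits in the SAP, and that isolated means bilirubin no higher than 43, bilirubin below 2xULN, and INR not above 1.5 if measured. The figure of 0 in 480 illustrates the rule and does not estimate missed cases in this trial. The cases would still be visible in listings, plots and the normal-range shift table. What is lost is a specified comparison between arms at xULN thresholds. The practical effect here is probably small, because the SAP suggests that no liver event had been reported.

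**What to change.** Keep the combined ALT row and the Hy's Law rows in SAP 12.7.1. Add stand-alone ALT categories at ≥3xULN, ≥5xULN and ≥8xULN, report them by arm in Table 3.29, and let them trigger Listing 18. Label them as laboratory threshold categories and not as stopping events: the protocol attaches persistence, symptom, monitoring or second-abnormality conditions to the 3x and 5x levels, and subjects there may continue treatment.

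Say also whether repeat tests at unscheduled visits count. SAP 12.4.2 keeps unscheduled visits out of summary tables, and the weekly repeats after a liver event would often fall between scheduled visits.

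If the limits are left unchanged, a sentence in the SAP should say that isolated ALT events are reported through the liver listings and plots, so that a zero in Table 3.29 is not read as an absence of ALT elevations.

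The cost is an edit to one table and a rerun of two displays, using data already collected and reference ranges that the laboratory supplies (Protocol 7.4.6). The downside is that some mild, transient ALT rises will be tabulated, and the ranges will differ from the SAP's current set. Because Protocol 5.2 excludes subjects with ALT above 2xULN at entry, a count at 3xULN should mostly reflect rises after screening. The change affects reporting only.
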